### 2. Objectives

The specific aims of the proposed RCT are to:

1. Test whether a nurse case management intervention will **increase linkage** of persons with HIV/HCV co-infection to an HCV treatment pathway via the Viral Hepatitis Center compared to enhanced usual care  
*H0:* A higher proportion of those who are randomized to the intervention arm will attend the Viral Hepatitis Clinic or enroll in an HCV-treating clinical trial within 60 days of randomization compared to those who receive enhanced usual care.
2. Determine if a nurse case management intervention will **decrease time to HCV treatment initiation** among persons with HIV/HCV co-infection compared to enhanced usual care

Date: May 8, 2017

Principal Investigator: [name], MPH, NP

Application Number: IRB00081068

*H0:* Those who are randomized to the intervention arm will have a decreased time to HCV treatment initiation from the point of randomization compared to those who receive enhanced usual care.

3. Describe the characteristics associated with uptake of HCV care among PLWH, controlling for covariates.

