### 3. Background

Linkage to HCV care among people co-infected with HIV/HCV is poor. The greatest gap in the United States HCV care cascade begins between diagnosis and linkage to care. Only 25% of PLWH with chronic HCV have attended an HCV appointment, and less than half of those have ever initiated HCV treatment. A large cohort study in Baltimore found that only 21% of injection drug users with HCV had ever seen an HCV specialist. At the Johns Hopkins Moore Clinic, less than half of patients who are referred to an HCV specialist by their primary care provider actually attend the scheduled specialty appointment.

The perceived threat of HCV and perceived need for HCV care among patients is low. This perception, coupled with the fact that HCV is a “silent epidemic”, places PLWH at great risk. Qualitative studies describe that the absence of HCV-related symptoms leads to little interest in receiving HCV treatment. This is exacerbated by a lack of knowledge about HCV and available therapies; horror stories about interferon-related side effects and old ineffective treatments dominate conversations among peers with HCV despite these barriers being minimized with new all-oral therapy. People with HCV also report low motivation to engage in HCV care due to competing demands from work, school or caregiving responsibilities. Therefore, interventions to increase HCV knowledge and motivation, such as education, patient navigation, and appointment reminders are needed to improve linkage to HCV care.

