Linkage to care will be defined as attendance at one or more appointment within the HCV treatment pathway via the Viral Hepatitis Center, including either traditional clinical care at the Bartlett Specialty Practice or an HCV treatment-providing clinical trial within the Viral Hepatitis Center. This will ensure that participants enrolled in the Care2Cure study have the opportunity to engage in HCV treatment in all pathways offered by the Viral Hepatitis Center and inherent in Johns Hopkins Hospital’s standard of care as an academic institution and research center. Independent of randomization allocation, all study participants will be asked in the baseline characteristic questionnaire if he/she would like to be referred to a clinical trial, with the option to refuse or opt out of trials for non-FDA approved treatments. Based on this participant preference, eligibility for actively recruiting clinical trials at the Viral Hepatitis Center will be assessed. Participants will then be referred by the study nurse case manager to either traditional care at the Bartlett Specialty Practice, a clinical trial with no investigational drug, or a clinical trial with an investigational drug, as eligible and available.

Multiple strengths support this approach to the outcome of linkage to care. In Maryland, patients must have a Metavir score greater than or equal to 2 to receive HCV treatment (Maryland Department of Health and Mental Hygiene, 2015). Linking patients to clinical trials that offer treatment to patients in all stages of liver disease, including F0 and F1, removes this barrier to treatment. This approach also minimizes selection bias. Participants who choose to receive HCV treatment through a trial may be different than those who seek care through the traditional clinical pathway; the Care2Cure study will include both.

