## 7. Study Statistics

### Analysis:

Data will be cleaned and efforts made to minimize the effects of missing data. All provider visits at Johns Hopkins are registered in the electronic medical record, so absence of a registered appointment during the study period will be considered non-attendance for the primary outcome variable. A computer-based data collection method will be used for data collection of independent variables in attempt to minimize missing data. Exploratory and descriptive analysis will be completed for all study variables. Variables will be tested for normality and examined with means and standard deviations or medians and interquartile ranges accordingly. Baseline characteristics comparing the two groups (usual care vs. intervention) will be assessed. Any differences between the groups will be adjusted for in further analysis. The significance level will be set at 0.05. All tests will be two-tailed and analyzed by intention-to-treat.

**Primary Outcome:** The primary outcome is linkage to care, measured by attendance at the Viral Hepatitis Center (either traditional care or an HCV-treating clinical trial) within 60 days of randomization (yes/no). This hypothesis will be tested using a two-sample z-test for the difference in independent proportions comparing the intervention to usual care groups.

**Secondary Outcome:** The secondary outcome is time to HCV treatment initiation, measured by the number of days from randomization to the date HCV treatment is initiated according to the medical record. Kaplan Meier estimates will be conducted to compare time to HCV treatment initiation between participants in the intervention group and the usual care group, and a log-rank test will be used to test the difference. Covariates (age, sex, race/ethnicity, HCV knowledge, substance use, fibrosis score, CD4+ T cell count, HIV viral load, care giving responsibilities, and participation in Cure Club) will be included in the Cox regression model. To account for a time to treatment initiation greater than the observed time period of 6 months, right censoring will be implemented for participants who have not initiated HCV treatment at the end of the 6-month period.

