### **Sample Size Justification:**

Currently, 40% of new Viral Hepatitis Clinic appointments are attended by patients. Based on prior studies testing the intervention components in similar populations, including persons living with HIV and/or substance use disorders, it is expected that the intervention will improve the primary outcome of linkage to care by 18-30%. Although the effect size is not known in the context of HCV, we estimate an improvement in linkage of 20% (i.e., 60% attendance [0.60] in the NCM group compared to 40% attendance [0.40] in the usual care group) based on these prior studies. Using these figures and a two-tailed test with an alpha of 0.05, a conservative estimate of the total sample size required to achieve 80% power is 97 per group, or a total of 194 participants (G\*Power 3.1.9.2). With a sample size of 100 participants in each group, there should be an adequate number of participants to detect a difference in proportion of linkage to care for the primary aim.

For Phase 2, participants with successful linkage to clinical care from Phase 1 (those who attend  $\geq 1$  appointment at the Viral Hepatitis Clinic within 60 days) will be included. Therefore, the eligible sample size will be less than 40-60% of the original sample size because a linkage to care proportion of 0.40-0.60 is expected, and some participants will link to a clinical trial and not be included in this outcome. This is a secondary outcome and estimated effect size is unknown. However, with 100 participants in this group (half of the total sample size), we will have 90% power to detect a hazard ratio of 2.

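### Time to HCV treatment initiation is restricted to 60-day clinic linkers in the sample-size text, against the randomised, intention-to-treat comparison in the Objectives and Analysis sections

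*Combined protocol and SAP*

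**What the plan says.** **Randomised comparison.** Section 2 (Objectives, Aim 2) states the hypothesis without a linkage condition: "Those who are randomized to the intervention arm will have a decreased time to HCV treatment initiation from the point of randomization". Section 7 (Analysis) counts days from randomisation, compares the intervention and usual care groups by Kaplan-Meier and log-rank, and adds a Cox model. It states "All tests will be two-tailed and analyzed by intention-to-treat" and "right censoring will be implemented for participants who have not initiated HCV treatment at the end of the 6-month period". It names no subset. Table 1 marks the 6-month treatment-initiation abstraction for all participants.

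**Restricted comparison.** Section 7 (Sample Size Justification) says: "For Phase 2, participants with successful linkage to clinical care from Phase 1" are included, defined as at least one Viral Hepatitis Clinic attendance within 60 days. It adds that "some participants will link to a clinical trial and not be included in this outcome". It puts the eligible number below 40-60% of the total, then takes 100 participants and states "we will have 90% power to detect a hazard ratio of 2".

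The Phase 2 procedures text and the Table 1 footnote limit who receives Phase 2. Only the Sample Size Justification limits who enters the outcome. Nothing reconciles the two sets.

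**The concern.** Linkage within 60 days is the primary outcome, and the trial is designed so that it differs between arms. Among intervention linkers there would be people who linked only because of the nurse; control linkers would have no counterpart to them. A log-rank or Cox comparison within linkers therefore loses the protection of randomisation. It also discards any benefit that arises because more people reach the clinic, which Aim 2 as worded would count.

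Leaving out those who link to trials adds a second selection. Trial referral is open to both arms ("Independent of randomization allocation, all study participants will be asked" about it at baseline), but calling a trial recruitment number with the participant belongs to the intervention only, so the excluded fraction may differ by arm.

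If the choice between the two sets is left until the data are seen, it could decide the Aim 2 conclusion. The stated power belongs to the restricted set and does not carry over to the randomised comparison.

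**Working it through.** **Inputs from the documents:** 100 per arm, 1:1; two-sided alpha 0.05; planned linkage 0.40 vs 0.60; HR 2, 90% power and 100 participants for the secondary outcome; censoring at 6 months. No 6-month initiation rate is given. The nearest figure, in Background, is historic: of those who had attended an HCV appointment, "less than half of those have ever initiated HCV treatment".

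**1. The plan's power figure.** Events for 90% power at HR 2:
- Schoenfeld, 1:1: 4 × (1.960 + 1.282)² / (ln 2)² = 87.5, so 88.
- Schoenfeld, 40:60: (1.960 + 1.282)² / (0.4 × 0.6 × (ln 2)²) = 91.1, so 92.
- Freedman: (1.960 + 1.282)² × (3/1)² = 94.6, so 95.

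If all 100 linkers start treatment, power is 91.5% (Freedman) or 93.4% (Schoenfeld, 1:1). The 90% is therefore reached only in the restricted set, and only if nearly everyone starts within 6 months. With linkers split 50/50 and control initiation p, intervention initiation at HR 2 is 1 − (1 − p)². Solving 50p + 50[1 − (1 − p)²] = 88 gives p = 0.80, hence 96% in the intervention arm.

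With 50% control initiation and the planned 40/60 split, events are 40 × 0.50 + 60 × 0.75 = 65 and power is 78%. If 20% of linkers go to trials, 80 people give 52 events and 69%.

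**2. Effect of the restriction, no Phase 2 effect.** Assumptions: 40% link in either arm, a further 20% link only with the nurse, and 50% of those who would link anyway start by 6 months. HR is the ratio of −ln(1 − proportion started). All-randomised control: 0.4 × 0.5 = 0.20. All-randomised intervention: 0.20 + 0.2x, where x is the starting rate in nurse-induced linkers. Linked-only: 0.50 vs (0.20 + 0.2x)/0.6.

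| x | All randomised | HR | Linked only | HR |
|---|---|---|---|---|
| 25% | 0.20 vs 0.25 | 1.29 | 0.50 vs 0.417 | 0.78 |
| 50% | 0.20 vs 0.30 | 1.60 | 0.50 vs 0.50 | 1.00 |
| 75% | 0.20 vs 0.35 | 1.93 | 0.50 vs 0.583 | 1.26 |

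A simulation agrees (linkage uniform on days 7-60, exponential initiation afterwards, censoring at day 180). Statistically significant apparent harm occurs in about 12% of trials of 100 per arm in the 25% case.

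**3. The same scenarios with a true Phase 2 HR of 2 (simulation).**

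| x | All-randomised HR | Power | Linked-only HR | Power |
|---|---|---|---|---|
| 25% | 2.17 | 84% | 1.49 | 32% |
| 50% | 2.68 | 97% | 1.98 | 75% |
| 75% | 3.05 | 99% | 2.42 | 93% |

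No direction reverses here, but the restricted estimate can miss the true Phase 2 effect on either side.

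**4. Leaving out trial linkers.** Assume 50% of linkers in each arm would start in clinic and trial linkers come from those who would not. Excluding 20% in both arms leaves HR 1.0. Excluding 10% of control and 30% of intervention linkers gives 0.5/0.9 = 0.556 vs 0.5/0.7 = 0.714, HR 1.54, with no true effect.

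**5. Power for all 200.** Here HR 2 is the overall effect between arms, not the Phase 2 effect of step 3. With control initiation q, events are 100q + 100[1 − (1 − q)²].

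| q | Events | Power |
|---|---|---|
| 10% | 29 | 46% |
| 20% | 56 | 74% |
| 30% | 81 | 88% |
| 33% | 88 | 90% |

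At q = 20% (40% linked, half start), 90% power needs an overall HR of about 2.3.

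**The case against.** The restriction stands in a sample-size paragraph, while the analysis text and Table 1 carry none, so it may never govern the analysis. Nor does the Analysis section literally say that all randomised participants are analysed. That is fair, but Aim 2 and the intention-to-treat statement have that plain meaning, and the sample-size text speaks of inclusion in the outcome and takes its power from the subset. It cannot be read as describing only who receives Phase 2.

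The linked-only question also looks deliberate. The procedures tie the 6-month review to measuring Phase 2, and they give a reason for leaving trial participants out of that phase. An all-randomised comparison cannot isolate Phase 2: with no Phase 2 effect its HR is still 1.3 to 1.9. This is a real trade-off. But the linked-only comparison does not isolate Phase 2 without bias either, and Aim 2 as worded asks about the whole intervention.

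The magnitudes rest on assumptions. The 10% vs 30% trial split is illustrative: no trial-linkage rate is given, and controls also receive a research hotline number and may be referred to trials. The 50% start rate adapts a historic figure for ever starting treatment. These points limit the precision of the sizes but leave the contradiction standing.

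Finally, this is a secondary outcome and the primary analysis is untouched. That is so, but it is the plan's only secondary outcome and the repair is cheap.

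**Conclusion.** The concern holds and should be fixed before analysis. The documents define two incompatible analysis sets for time to treatment initiation. The one in the Sample Size Justification selects on a post-randomisation outcome planned to differ by 20 percentage points between arms, and it does not answer Aim 2 as worded.

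Under the assumed linkage and initiation rates, with no Phase 2 effect, the restricted HR ranges from 0.78 to 1.26 where the randomised comparison gives 1.29 to 1.93. The direction of bias cannot be known in advance, and significant apparent harm would be uncommon. The 90% power statement is unsupported as written: it requires 88 to 95 starts among 100 linkers, although the same paragraph says that trial linkers will reduce that number. Analysing all 200 does not by itself secure 90% power; that depends on the initiation rate, which the plan must state.

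**What to change.** Reconcile the Sample Size Justification with the Analysis and Objectives sections:

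1. Define the secondary analysis set as all randomised participants, with time from randomisation and non-initiators, including never-linkers and late linkers, censored at 6 months.
2. State in advance how treatment started inside a clinical trial is handled, and justify it as a choice of estimand. One option is to count it as an event, since Aim 2 does not limit the route, with a sensitivity analysis censoring at trial enrolment because the procedures expect a different timeline there. The essential point is that the rule is fixed beforehand.
3. Keep the linked-to-clinic comparison only as a supportive analysis, labelled non-randomised.
4. Replace the 90% power sentence with an events-based figure for all 200, stating the assumed control initiation rate and whether the HR is the overall or the Phase 2 effect.

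The cost is a protocol/SAP amendment. Sample size and visits do not change, and the 6-month abstraction already covers everyone. Treatment start dates may have to be requested from trial coordinators, who under the present text confirm attendance only, unless the medical record already holds them.

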X=all participants; I=intervention arm only; appt.= appointment; NCM=nurse case management; aART change appointment with HIV provider; bParticipants will be encouraged to call the research nurse case manager for needs relating to linking to HCV care and initiating HCV treatment; cAppointment reminders will occur 1 day and 1 week (if applicable) before HCV appointment; dIncludes participants from Phase 1 who link to an HCV provider only

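### The 90% power for a hazard ratio of 2 needs 88 to 95 treatment starts among 100 linked participants, and no 6-month initiation rate supports that count

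*Combined protocol and SAP*

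**What the plan says.** Section 7, Sample Size Justification, restricts the Phase 2 comparison to participants who link to clinical care. It says that "the eligible sample size will be less than 40-60% of the original sample size", because linkage of 0.40 to 0.60 is expected and "some participants will link to a clinical trial and not be included in this outcome". It adds: "This is a secondary outcome and estimated effect size is unknown". It then states that "with 100 participants in this group (half of the total sample size), we will have 90% power to detect a hazard ratio of 2". The sentence comes with no event count, initiation proportion, censoring assumption or formula.

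Section 7, Analysis, sets a two-tailed 0.05 level. Under Secondary Outcome it specifies a log-rank test on days from randomization to treatment start, and "right censoring will be implemented for participants who have not initiated HCV treatment at the end of the 6-month period". Footnote d of Table 1 describes Phase 2 in the same restricted way: "Includes participants from Phase 1 who link to an HCV provider only". The Analysis paragraph also says "All tests will be two-tailed and analyzed by intention-to-treat", which points to all 200 randomised.

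**The concern.** Only a treatment start within 6 months is an event. Everyone else is censored and adds almost nothing to log-rank power. A power figure that rests on 100 participants therefore holds only if nearly all of them start.

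The plan's own text does not support that:

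- With 100 per arm and linkage of 40% and 60%, the 100 is simply 40 + 60 linkers, before the trial exclusions that the same paragraph expects.
- Phase 1 (Section 4) cites a Maryland fibrosis threshold for receiving treatment.
- Phase 2 (Section 4) allows the HCV provider to defer treatment.
- Section 3 expects many participants to need a change of HIV regimen. Section 4 gives a usual wait of 3 to 6 months for the next HIV visit and a viral load recheck 4 to 8 weeks after the change.
- Section 3 reports that fewer than half of people with HIV who attended an HCV appointment had ever started treatment. The Abstract gives about 7% of those with chronic HCV. These are background figures rather than 6-month rates, but they are far below 88 to 95%.

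At stake is how a null result on specific aim 2 would be read. A reader told that power was 90% would take it as fair evidence against a hazard ratio of 2, when the chance of missing such an effect could be two to four times the stated 10%.

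**Working it through.** **Inputs.** Two-sided alpha 0.05, log-rank test and censoring at 6 months (Section 7, Analysis and Secondary Outcome). Hazard ratio 2, 90% power, 100 participants, linkage 0.40 and 0.60 (Sample Size Justification). Initiation rates are not in the plan and are assumed below.

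**Events needed for 90% power.** (1.960 + 1.282)² = 10.51 and (ln 2)² = 0.480.

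- Schoenfeld, 1:1: 10.51 / (0.25 × 0.480) = 87.5, so 88.
- Schoenfeld, 40:60: 10.51 / (0.24 × 0.480) = 91.1, so 92.
- Freedman: 10.51 × [(2 + 1)/(2 − 1)]² = 10.51 × 9 = 94.6, so 95.

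**Reproducing the stated figure.** If all 100 participants are events, power is 93.4% (Schoenfeld 1:1), 92.4% (Schoenfeld 40:60) or 91.5% (Freedman). The 90% is thus reproduced only when nearly every participant is an event.

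**Initiation this implies.** Let p be the proportion of usual-care linkers who start by 6 months. Under proportional hazards with a hazard ratio of 2, the intervention proportion is 1 − (1 − p)².

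- 1:1: p = 0.80 gives 50 × 0.80 + 50 × 0.96 = 88 events.
- 40:60: p = 0.83 gives 40 × 0.83 + 60 × 0.97 ≈ 91.5 events.

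So about 80 to 83% of usual-care linkers and 96 to 97% of intervention linkers must start.

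**Power at lower initiation.** With a the usual-care share of the set and d = n₀p + n₁[1 − (1 − p)²], power = Φ(√(d·a(1 − a)) × ln 2 − 1.96). The simulated column is a log-rank test on exponential times censored at 6 months.

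| p (assumed) | Events, 40 + 60 | Schoenfeld power | Simulated power | Schoenfeld power, 36 + 54 |
|---|---|---|---|---|
| 20% | 30 | 46% | about 40% | 42% |
| 30% | 43 | 60% | about 55% | 56% |
| 40% | 54 | 71% | about 67% | 66% |
| 50% | 65 | 78% | about 75% | 74% |
| 70% | 83 | 87% | about 85% | 83% |

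The last column assumes that 10% of linkers go to a clinical trial, which leaves 90. Even if all 90 start, power is 89.6%.

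**Top of the plan's effect range.** The paragraph expects that "the intervention will improve the primary outcome of linkage to care by 18-30" percent. At 40% and 70% linkage there are 110 linkers, and Schoenfeld power at p = 20%, 30%, 50% and 70% is 48%, 63%, 81% and 89%.

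**All 200 randomised.** With 40% and 60% linkage, a hazard ratio of 2 among linkers, and non-linkers never starting, simulated power is about 79% at p = 20%, 91% at 30%, and 96 to 98% at 40 to 70%. This contrast also contains the linkage difference.

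**Timeline check.** For a usual-care participant who needs a regimen change, the wait plus the recheck runs from about 91 + 28 = 119 days to 183 + 56 = 239 days, against a cut-off near 183 days.

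**The case against.** The formula is not wrong. Entering 100 events returns slightly more than 90%, so this could be called an unstated assumption rather than an arithmetical error. The plan names no method for the figure, so how it was obtained cannot be known. That stands, and the claim here is about what 90% requires.

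The loss is small when initiation is high: at 70% of usual-care linkers, Schoenfeld power is 87%. The fibrosis restriction and the trial exclusions may partly remove the same patients. The timeline affects only those who need a regimen change, its lower end lies inside 6 months, and Section 4 judges 6 months adequate. These points also stand. They limit how far the shortfall can be pinned down, but they supply no expected proportion starting.

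The strongest objection is the analysis set. Under intention-to-treat with all 200, power reaches 90% from about 30% initiation among usual-care linkers. But the power sentence is explicitly about the 100 linkers, and the all-200 contrast is a different comparison. The objection is a reason to name the set, not a defence of the sentence.

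The plan does say that the effect size is unknown and the outcome secondary. That qualifies the hazard ratio, not the number of events.

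**Conclusion.** The concern holds. As written, the 90% is unconditional, yet it requires 88 to 95 treatment starts out of 100 linked participants within 6 months, and the documents give no basis for that count. For 100 linkers split 40:60, the chance of missing a true hazard ratio of 2 is about 22% at 50% usual-care initiation and 40% at 30% (Schoenfeld), or about 25% and 45% by simulation, rather than 10%. Trial exclusions lower power further.

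The size is a range because the initiation rates are assumptions. It also rests on proportional hazards and on the linked-only set. If all 200 are analysed, a shortfall appears only at low initiation. The outcome is secondary, and the primary sample size is unaffected.

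**What to change.** Replace the last sentence of the Sample Size Justification with an event-based statement: at two-sided 0.05, 90% power for a hazard ratio of 2 needs 88 treatment starts at 1:1, or 92 at 40:60. Then give:

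- the analysis set to be used, linked participants or all 200 randomised;
- the number of linkers expected after trial exclusions, where the linked set is used;
- the assumed 6-month initiation proportion in each arm, and the expected events;
- the resulting power, or the detectable hazard ratio, over a range such as 20 to 70% usual-care initiation.

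This costs one paragraph of protocol text. Enrolment, test, endpoint and follow-up do not change. The price is that the stated power becomes conditional and, for the linked-only set, probably less favourable.
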